## 1. SUMMARY

Recent studies have shown the impact of eating patterns on lung function. However, the specific benefits of the Mediterranean Diet (MD) in preventing pulmonary dysfunction are not well known.

**Objective.** To evaluate the effect of MD adherence on the deterioration of lung function in smokers.

**Methodology.** Design: Controlled, parallel, multicenter, cluster-randomized clinical trial. Participants: 750 active smokers aged 25 to 75 years with a cumulative consumption of more than 10 packets/year, without previous respiratory disease and who agree to the conditions of the study and sign an informed consent to participate. Scope: 20 Primary Care Centers managed by the Catalan Health Institutes in Tarragona Province, to be randomly assigned to a control or an intervention group (1:1). All participants will receive advice to quit smoking. Intervention: A 2-year nutritional intervention designed to increase MD adherence. Elements include: 1) annual visit to deliver personalized nutritional education, 2) annual telephone contact to reinforce the intervention, and 3) access to an ad hoc online dietary blog. Control group: Continuation of usual diet pattern. Assessment (both groups, initially and annually for two years): a) pulmonary function, evaluated by forced spirometry and b) adherence to the MD, evaluated by a 14-item questionnaire and medical tests. Statistical analysis: Intention-to-treat basis, with the individual smoker as unit of analysis. Pulmonary function and adherence to a Mediterranean-style diet in both groups will be compared.

**Expected results.** MD adherence prevents the deterioration of lung function in smokers without previous respiratory disease. Thus, MD is key to pulmonary disease prevention, together with the recommendation of smoking cessation.

## 2. ABBREVIATIONS

PCC: Primary care center

MD: Mediterranean diet

FEV1: Expiratory flow in the first second

FVC: Forced vital capacity

ICS (Catalan acronym): Catalan Institute of Health

IDIAP - Jordi Gol (Catalan acronym): Research Institute for Primary Care - Jordi Gol

BMI: Body mass index

COPD: Chronic obstructive pulmonary disease

MEDISTAR: MEditerranean Diet and Smoking in Tarragona and Reus

AbC: Abdominal circumference

PERIS (Catalan acronym): Strategic Plan for Research and Innovation in Health

DCQ: Data collection questionnaire

RESET: REsults of Spirometry to Encourage Tobacco cessation

### **3. PROJECT DESCRIPTION**

#### **3.1. BACKGROUND OF THE TOPIC**

Nutrition and dietary habits are recognized factors in the development, progression, and prevention of chronic pathologies such as cancer and cardiovascular diseases [1,2]. However, the impact of diet on lung function and respiratory diseases is not as well established [3].

In our environment, smoking is the main factor in the etiopathogenesis of respiratory pathology, although other factors may also be involved, such as environmental agents, respiratory infections, genetic disorders, and dietary habits [4]. Inhalation of tobacco smoke particles accelerates the physiological decline of lung volume attributable to aging and increases susceptibility to respiratory dysfunction [5]. For years, it has been known that tobacco smoke generates thousands of free radical particles, an important source of oxidative stress and inflammation.

This effect can be neutralized by the action of enzymatic antioxidants such as superoxide dismutase, catalase, or glutathione peroxidase. Dietary intake of other antioxidants also may have a protective effect on lung function [6]. Specifically, evidence of the protective action of certain food and nutrients on pulmonary ventilation parameters such as forced vital capacity (FVC) and expiratory flow in the first second (FEV1) has been reported [7]. Thus, consumption of fruits and vegetables with a high content of antioxidant vitamins, phenolic compounds, minerals, and dietary fiber has a positive effect on respiratory health [8-9]. Omega-3 fatty acids present in blue fish and shellfish have beneficial effects on the inflammatory mechanisms involved in the pathophysiology of chronic obstructive pulmonary disease (COPD) [10]. In contrast, high consumption of processed meat has been associated with worse pulmonary function and increased risk of COPD [11-12]. Also, low or moderate alcohol consumption has been associated with better lung function, while excessive intake has detrimental effects [13-14].

Although the evaluation of the effect of individual foods has been valuable, it presents conceptual and methodological limitations because the diet contains a variety of foods that may interact, with varying effects [15]. Therefore, analysis of dietary patterns is now considered to offer a better approximation to the study of the effects of food on health. Available evidence shows that the "western" diet with high consumption of fried and processed foods, processed meats, refined sugars, and sweets increases the risk of COPD [16-17] and that a "healthy" diet rich in whole grains, vegetables, fruits, and fish is associated with better lung function [18]. In this context, our group carried out a pioneering observational study that found a Mediterranean-type pattern is more likely to preserve lung function in smokers without previous respiratory disease, compared to a western diet, and a pattern of alcohol use was associated with an increased probability of functional impairment [19-21]. Therefore, adherence to a healthy dietary pattern, in addition to smoking cessation, offers new perspectives on avoiding the preventable loss of lung function in smokers.

The traditional dietary pattern of Mediterranean countries includes a set of characteristic foods with beneficial effects on inflammation and oxidation, such as legumes, fresh fruits and vegetables, blue fish, olive oil and nuts. The MD is rich in antioxidants (vitamin C and E, beta-carotene and folates), phenolic compounds (the most abundant being flavonoids), and monosaturated and polyunsaturated fatty acids [22]. This pattern has been associated with the reduction of cardiovascular events and all-cause mortality, and for years has been recommended in cardiovascular prevention. Extending this recommendation to respiratory pathology related to smoking is of evident interest in primary prevention.

To our knowledge, no national or international groups are currently working on the protective effects of MD in preventing respiratory diseases. Therefore, a clinical trial is presented with the objective of evaluating the impact on lung function of an intervention to increase MD adherence in a cohort of smokers without previous respiratory pathology.

### **3.2. PRELIMINARY RESULTS**

The present study is part of a broader program to reduce smoking behaviors developed by the Study Group on Respiratory Pathology in Tarragona, accredited by IDIAP Jordi Gol (the Catalan acronym for the Jordi Gol Institute for Primary Care Research). The RESET study is a clinical trial on smoking cessation, designed to evaluate the efficacy of a motivational intervention based on information obtained from spirometry (Project FIS PI 11/01962) [19]. Within the RESET study, a two-phase project was designed. In the first phase, the RESET-DIET observational study, researchers identified the main dietary patterns present in the smoking population attended at primary care centers (PCCs) in Catalonia, and examined their association with lung function. Their results are already in an advanced stage of publication [20-21].

The RESET-DIET study identified three main dietary patterns: alcohol consumption (wine, beer and distillates), a westernized pattern (red and processed meat, dairy products and sugary drinks) and a Mediterranean pattern (poultry, eggs, fish, vegetables, legumes, potatoes, fruit and nuts). Multivariate analysis associated changes in respiratory function with the alcohol consumption pattern in both men and women (OR 4.56, 95% CI 1.58-13.18) and with the westernized pattern only in women (OR 5.62, 95% CI 1.17-27.02). In contrast, the Mediterranean pattern trended toward an inverse association with functional deterioration, without reaching statistical significance (OR 0.71, 95% CI 0.28-1.79) [20]. It was also observed that the inverse relationship with lung function is influenced by personal characteristics, such as abdominal obesity, especially in men [21].

These findings suggest that certain personal characteristics and dietary patterns in the smoking population are associated with impaired lung function. In addition to recommending smoking cessation, health professionals should consider an intervention regarding dietary factors. This is precisely the basis for the second-phase project, the MEDISTAR study (Mediterranean Diet and Smoking in Tarragona and Reus), detailed in the following section.

### **3.3. HYPOTHESIS AND OBJECTIVES**

#### **3.3.1. Hypothesis**

Increased adherence to the MD pattern in addition to smoking cessation advice, will prevent the impairment of lung function in smokers without respiratory disease.

#### **3.3.2. Primary objective**

To evaluate the effect of MD adherence on the deterioration of lung function in smokers without previous respiratory disease treated in Tarragona PCCs.

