#### **3.3.3 Secondary objectives**

In smokers without previous respiratory disease:

- 1) To evaluate the effectiveness of a multicomponent nutritional educational intervention designed to increase adherence to the MD pattern.
- 2) To study the relationship between lung function and anthropometric parameters such as the abdominal circumference (AbC) and body mass index (BMI).
- 3) To study the relationship between lung function and various markers of food consumption, inflammation and oxidation.

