#### **4.4. INTERVENTIONS**

Participating centers will be assigned randomly to a control or intervention group (1:1). Volunteers will be referred to an initial visit (V0) to confirm inclusion criteria and sign an informed consent (Annex 1). Basal variables will be collected at that time.

Participants from the intervention PCCs will enter into an educational program to increase adherence to the MD. It will consist of five contacts that integrate three operational components:

- a) Explain the details of the MD and the benefits of following this dietary pattern in an individual visit of 25-30 minutes (V1). Data on the study variables will be collected and medical tests will be performed. This data gathering will be repeated annually for two years (V3 and V5).
- b) Clarify any doubts about following the MD pattern and other advice received, in a telephone conversation. This annual contact will reinforce the intervention (V2 and V4).
- c) Provide information about MD foods, cooking tips, adapted recipes, and other related topics in an ad hoc nutrition blog.

The control group will carry out the same 5 visits (3 individual visits and 2 phone calls), although no changes will be made in their usual diet and they will not be provided with access to the nutritional blog.

All participants will receive health advice to stop smoking, according to the protocol recommended to health professionals in Catalonia: a proposal of smoking cessation expressed in a clear, firm, and personalized way, in an empathic and respectful setting.

At the end of the study, if the intervention is effective, control group members will be invited to participate in the same intervention program.

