#### **4.5. DATA COLLECTION**

All the information will be collected in a computerized data collection questionnaire (DCQ), only accessible from the administrators of the ICS corporate Intranet in Tarragona. Access will be restricted and controlled by a personal password for each researcher, who will be responsible for entering participant data.

This DCQ will include initial information (V0):

- Socio-demographic data (age, sex, marital status, number of children, level of education, social class)
- Medical history and respiratory symptomatology (dyspnea, cough, expectoration, chest pain, other symptoms)

At follow-up visits (V1, V2 and V3), the following information will be obtained:

- Physical examination (weight, height, BMI, blood pressure, and level of exhaled carbon monoxide determined by CO-oximetry)
- Smoking habit (accumulated consumption, current consumption, nicotine dependence, motivation to quit smoking)
- Alcohol consumption
- Physical Activity Classification Questionnaire [24]
- Food frequency questionnaire to assess food consumption [25]
- MD adherence, based on 14-item questionnaire [26]
- 12-lead electrocardiogram
- Forced spirometry and bronchodilator test to measure FVC, FEV and the ratio between them (FEV1/FVC).
- Levels of glucose, total cholesterol and fractions, triglycerides, creatinine and transaminases (serum, autoanalyzer)

- Serum inflammation markers: high-sensitivity C-reactive protein and interleukin-6 (serum, autoanalyzer and assay ELISA)
- Oxidation markers: oxidized LDL in plasma (plasma EDTA, assay ELISA)
- Food consumption markers: excreted of total polyphenols (fresh urine, Folin-Ciocalteau)

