#### **4.7. STATISTICAL ANALYSIS**

Data will be extracted from the centralized database for blinded analysis, based on intention to treat. The efficacy of randomization will be assessed by comparability and homogeneity of the intervention and control groups. Losses to follow-up will be calculated for each group and evaluated to determine whether the proportion of losses is independent of assignment to the intervention or control group.

Qualitative variables will be described as frequencies or percentages, and quantitative variables by the mean and standard deviation or interquartile range. Analysis will be stratified by study groups and compared at basal level using the  $\chi^2$  test for qualitative and the Student t or Mann-Whitney U test for quantitative variables.

Pulmonary function, anthropometric data, foods consumed, and MD adherence at V1 will be compared to values obtained at the final visit (V5). A multivariate analysis will be performed to determine the factors independently associated with the observed changes, adjusting for relevant covariates. The results will be presented as

hazard ratios, with 95% confidence intervals. All analysis will be performed with the SPSS v22.0 program, considering a p-value <0.05 statistically significant.

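### The primary objective is worded as the effect of diet adherence, but only the education programme is randomised, and the analysis section specifies no between-arm estimate of the outcome

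*Combined protocol and SAP*

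**What the plan says.** **The question.** Section 3.3.2 gives the primary objective as "To evaluate the effect of MD adherence on the deterioration of lung function in smokers without previous respiratory disease". The hypothesis in section 3.3.1 likewise credits greater adherence, on top of quitting advice, with the protection. The expected result in the summary is that "MD adherence prevents the deterioration of lung function in smokers without previous respiratory disease".

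**What is randomised.** Under section 4.4, centres are allocated 1:1, and "Participants from the intervention PCCs will enter into an educational program to increase adherence to the MD". Control participants have the same number of visits and calls but keep their usual diet. The programme appears among the objectives only as secondary objective 1 in section 3.3.3: "To evaluate the effectiveness of a multicomponent nutritional educational intervention designed to increase adherence to the MD pattern".

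**How adherence arises.** Section 4.5 lists "MD adherence, based on 14-item questionnaire" among the data collected at visits. The schedule in section 5 places the food questionnaires at V1, V3 and V5, all after centres have been allocated.

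**The analysis.** The main variable (section 4.6) is a yes/no composite of impaired lung function at the end of follow-up. Section 4.7 promises intention to treat, group comparisons at baseline, a comparison of V1 with V5 values, and one model: "A multivariate analysis will be performed to determine the factors independently associated with the observed changes, adjusting for relevant covariates". The summary adds that lung function and diet adherence in the two groups will be compared.

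**The concern.** Allocation protects one comparison: intervention centres against control centres. Intention to treat therefore estimates the effect of assignment to the programme. Adherence at follow-up is partly a result of that assignment and partly the participant's own choice, so comparing people who did and did not change their diet is not protected by randomisation.

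The objective asks about adherence, while the design answers a question about the programme. The analysis section does not close the gap. It names no test or model of the outcome between arms at follow-up, and its single model is framed as a search for associated factors. If adherence enters that model, its coefficient is an observational association. RESET-DIET already supplied evidence of that kind (section 3.2: odds ratio 0.71, 95% CI 0.28 to 1.79, for the Mediterranean pattern), and a trial is run to improve on it.

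At stake are two things. One is what the primary estimate is, and hence which result decides the trial. The other is whether a difference between arms would be reported as proof that adherence itself protects the lung, which needs assumptions beyond randomisation.

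**Working it through.** **1. Question, design and analysis side by side**

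| Element | Place | Content |
|---|---|---|
| Primary question | 3.3.2, 3.3.1, summary | Effect of adherence |
| Randomised factor | 4.4 | Education programme or usual diet, by centre |
| Adherence | 4.5, section 5 schedule | Measured after allocation |
| Primary endpoint | 4.6 | Impaired lung function at end of follow-up |
| Tests between groups | 4.7 | Specified at baseline only |
| Change over time | 4.7 | V1 against V5 |
| Model | 4.7 | Factors associated with change; covariates not named; role of arm not stated |
| Comparison of groups on outcome | Summary | Stated, no method given |

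The one model specified is not described as estimating the randomised contrast, and it cannot give a randomised answer about adherence. No method that uses allocation to study adherence is described.

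**2. The plan's own sample size (section 4.3)**

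Inputs: proportions 0.17 and 0.31, two-sided alpha 0.05, power 80%, loss 25%.

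- h = 2·asin(√0.31) − 2·asin(√0.17) = 0.331
- n = 2·((1.960 + 0.842)/0.331)² = 143.3, rounded up to 144 per group
- 144/(1 − 0.25) = 192 per group, as stated

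The final step, to 750 with a design effect of 1.7, does not follow exactly (2 × 192 × 1.7 = 653). Nothing here depends on that.

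**3. Illustration: what separates the two questions**

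Effective number per arm = 375 × 0.75/1.7 = 165.4. Power = Φ(h·√(165.4/2) − 1.96), with 0.31 in controls.

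| Between-arm difference | Intervention proportion | Power |
|---|---|---|
| 14 points, as planned | 0.17 | 85% |
| 7 points: half of it (assumed) | 0.24 | 30% |
| 4.2 points: 30% of it (assumed) | 0.268 | 13% |

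The 7-point row assumes that 14 points is the effect in people who change diet and that the programme changes diet in half. The 4.2-point row assumes that 70% of the arm effect runs through adherence and that follow-up adherence is then adjusted for. Neither the 50% nor the 70% is in the documents.

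**4. Illustration: using allocation as instrument**

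On the 7-point row, the standard error of the difference is √((0.31·0.69 + 0.24·0.76)/165.4) = 0.0489. Dividing by an assumed 0.5 difference in diet change gives 0.07/0.5 = 0.14, standard error 0.0489/0.5 = 0.098, and a 95% CI of about −5 to 33 points. The estimate returns 14 by construction; only the width is informative. The example also treats diet change as yes/no. With the 14-item score as exposure, the effect would be per score point, and its size cannot be worked out from the documents.

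**The case against.** The strongest reply is that the authors plainly mean the programme. The end of section 3.1 describes a trial of an intervention to raise adherence. Section 4.1 speaks of the effect of increasing adherence. Section 4.4 makes an offer to controls depend on whether the intervention works, and section 6 refers to demonstrating its efficacy. With intention to treat stated twice and the summary comparing the groups, section 3.3.2 looks like shorthand. Most of this stands. A reader might infer that the primary question can be answered only by a confounded association or by an arm effect adjusted for its own consequences. The documents do not support that, because a between-group intention-to-treat comparison is announced. What remains is that the formal objective, the hypothesis and the expected conclusion all say adherence, and that section 4.7 does not turn the announced comparison into a specified analysis.

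Second, nothing says that follow-up adherence, weight or smoking status will enter the model, or even that arm will. That stands too. Adjustment for consequences of the programme is not planned; it is merely not ruled out.

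Third, section 4.3 attaches 0.17 and 0.31 to the two groups, so 14 points can be read as the planned difference between arms. The figures are cited to an observational study of dietary patterns, so their origin is not settled by the documents. Either way, rewording the objective would not change the power.

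Fourth, a null result would not be uninterpretable: the summary compares adherence between groups, and secondary objective 1 concerns the programme's effectiveness. A failure to change diet would show.

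**Conclusion.** The point holds as a mismatch between the worded objective and the randomised contrast, together with an unspecified primary between-arm analysis. It rests on the text alone and needs no numerical assumption.

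Its size lies in what can be concluded. As written, a difference between arms could be reported as an effect of adherence, or an observational coefficient could be offered as the answer to the primary objective. It is not a numerical error, and the 192 per group is correct on its inputs.

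A reader might go further and take the 30% or 13% power as the trial's true power. Those figures reproduce, but they rest on unsourced shares of 50% and 70%, and the 13% describes a model that the plan does not contain. They are illustrations, not consequences of the plan. Nor do the documents establish that an instrumental-variable analysis is required: labelling adherence analyses as observational would be enough.

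**What to change.** 1. **Objective and estimate (sections 3.3.1, 3.3.2 and summary).** Restate the primary objective as the intention-to-treat effect of assignment to the programme, intervention against control centres, on impaired lung function at V5.
2. **Primary model (section 4.7).** Specify a between-arm model that accounts for centre. Adjust only for values measured before the intervention starts: baseline spirometry, age, sex and pack-years. State that follow-up adherence, weight and smoking status are not covariates. Name the baseline spirometry used: the schedule puts it at V0, while section 4.7 starts its comparison of pulmonary function at V1. Any V1 value used must be recorded before the education begins.
3. **Associated-factors model.** Report it separately from the arm effect and label it observational.
4. **Conclusions.** Do not word an intention-to-treat result as an effect of adherence; revise the expected-results sentence to match.
5. **Optional.** If the effect of adherence is wanted, use allocation as instrument in a secondary analysis, expressed per point of the 14-item score and with inference suited to 20 centres. State the assumption that the programme acts on lung function only through diet.

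Items 1 to 4 cost wording and one specified model, on data already to be collected. Item 5 is a trade-off: its interval is likely to be wide, and its key assumption cannot be verified from the trial data.
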